# The HOPES Trial Version 5 02/23/2018

the CSF sample drawn from the port with a sterile syringe. CSF will be centrifuged (4°C, 1,459 X g for 10 minutes) and portioned into aliquots and frozen at -80°C; any residual sample will be frozen at -80°C for future study. The CSF pellet should be covered in a 10% DMSO solution (e.g., 100µl CSF plus 11µl DSMO) and frozen at -80°C and transferred to -145°C after 24hrs when possible.

Samples will be labeled with bar-coded subject study identification numbers, sample type and time point. They will be stored indefinitely at the University of Texas Health Science Center at Houston, Neuroscience Research Repository, [name] Laboratory, The Vivian L. Smith Department of Neurosurgery,

6.3.9 Adherence Assessments. Temperature will be monitored for adherence to study assignment.

#### 7. **MANAGEMENT OF ADVERSE EXPERIENCES**

Adverse events will be graded according to the USDHHS Common Terminology Criteria for Adverse Events V4.0 (USDHHS, Table 2) and summarized according to body system. Primary focus for analysis will be on 6-month mortality rate, incidence of pneumonia, incidence of DVT/PE, incidence of bleeding and incidence of arrhythmia. For the purpose of safety monitoring, adverse events in the table below of Grade 3 or higher will be classified as "Important AEs" or selected AEs of interest.

Table 2. Selected AEs	Table 2. Selected AEs from USDHHS Common Terminology Criteria for Adverse Events V4.0 USDHHS									
Adverse Event	Grade 1	Grade 2	Grade 3	Grade 4	Grade 5					
Sinus Bradycardia	Asymptomatic, intervention not indicated	Symptomatic, medical intervention indicated	Severe, medically significant, medical intervention indicated	Life-threatening consequences; urgent intervention indicated	Death					
Supraventricular tachycardia	Asymptomatic, intervention not indicated	Non-urgent medical intervention indicated	Medical intervention indicated	Life-threatening consequences; hemodynamic compromise; urgent intervention indicated	Death					
Ventricular arrhythmia	Asymptomatic, intervention not indicated	Non-urgent medical intervention indicated	Medical intervention indicated	Life-threatening consequences; hemodynamic compromise; urgent intervention indicated	Death					
Thromboembolic event	Venous thrombosis (e.g., superficial thrombosis)	Venous thrombosis (e.g., uncomplicated deep vein thrombosis),	Thrombosis (e.g., uncomplicated pulmonary embolism [venous],	Life-threatening (e.g., pulmonary embolism, cerebrovascular event, arterial	Death					

			1	02/23/	2018                                    
		medical intervention indicated	nonembolic cardiac mural [arterial] thrombus), medical intervention indicated	insufficiency); hemodynamic or neurologic instability; urgent intervention indicated	
Pneumonia			Dyspnea and pneumonia symptoms (e.g., aspiration pneumonia); hospitalization indicated; unable to aliment orally	Life-threatening respiratory or hemodynamic compromise; intubation or urgent intervention indicated	Death
Pulmonary edema	Radiologic findings only; minimal dyspnea on exertion	Moderate dyspnea on exertion; medical intervention indicated; limiting instrumental ADL	Severe dyspnea or dyspnea at rest; oxygen indicated; limiting self care ADL	Life-threatening respiratory compromise; urgent intervention or intubation with ventilatory support indicated	Death
Bleeding/hemorrhage	Mild; intervention not indicated	Moderate symptoms; medical intervention or minor cauterization indicated	Transfusion, radiologic, endoscopic, or elective operative intervention indicated	Life-threatening consequences; urgent intervention indicated	Death
Intraoperative hemorrhage			Postoperative radiologic, endoscopic, or operative intervention indicated	Life-threatening consequences; urgent intervention indicated	Death
Infection (culture positive) (e.g., blood stream infection, urinary tract infection, ventriculitis)		Oral intervention indicated (e.g., antibiotic, antiviral)	IV antibiotic, antifungal, or antiviral intervention indicated; radiologic, endoscopic, or operative intervention indicated	Life-threatening consequences; urgent intervention indicated	Death
Device-related infection			IV antibiotic, antifungal, or antiviral intervention indicated; radiologic or operative	Life-threatening consequences; urgent intervention indicated	Death

		intervention indicated	
Death			Death

# 8. CRITERIA FOR INTERVENTION DISCONTINUATION

Subjects may be discontinued from hypothermia at any time for patient safety per the decision of the site PI.

#### 9. STATISTICAL CONSIDERATIONS

# 9.1 General Design Issues

This is a randomized study of hypothermia for patients with traumatic brain injury. The primary hypothesis of the study is that early induction and maintenance of hypothermia in patients with traumatic brain injury undergoing hematoma evacuation will improve global neurologic outcome. Global neurologic outcome will be assessed using the Glasgow Outcome Scale (GOSE). The primary outcome measure is the GOSE at 6 months.

#### 9.2 Outcomes

**9.2.1 Primary outcome**. Primary outcome is GOSE at 6 months±3weeks post injury. GOSE (dichotomous: Good recovery and moderate disability will be designated as favorable outcomes; severe disability, vegetative state, and death as poor outcomes) at 6 months post-injury will be the primary outcome. Disability Rating Scale (DRS) at 4-6 weeks will be used to impute missing GOS/GOSE scores for futility analysis. Outcome scales will be assessed by an evaluator who is blind to study group assignment.

Glasgow Outcome Scale-Extended (GOSE) is a widely used global outcome score including 8 categories: dead, vegetative state, lower/upper severe disability, lower/upper moderated disability, lower/upper good recovery(47). GOSE assesses consciousness, independence, work status, return of lifestyle via a structured interview. It is relatively easy to administer and has good interrater reliability and content validity. (Appendix II)

Disability Rating Scale (DRS) is a global outcome scale that measures the level of arousal, cognitive ability related to activities of daily living and level of functioning. It includes eye opening, communication ability, motor response, feeding, toileting, grooming and employability(48). Scores range from 0 (no disability) to 29 (profound vegetative state) and death is scored at 30. It has been shown to be a good predictor of later outcome with the one month exam having an 87% correlation with the 6 month GOSE(12). (Appendix III)

#### **9.2.2 Secondary outcomes.** Secondary outcomes will include:

- adverse event rates (e.g., infection, pneumonia, hemorrhage, thrombosis)
- ICU LOS, hospital LOS
- incidence of cortical spreading depolarization

• levels of biomarkers (e.g., GFAP, UCH-L1)

#### 9.3 Sample Size and Accrual

A randomized design will be used in this study. Enrollment is intended to be N=120 but the trial allows an extension to a maximum of 350 patients randomized equally at a 1:1 ratio to each of two arms (hypothermia versus control). The final analysis will use a one-sided Fisher's exact test with significance level of 0.02 to compare proportions of patients with good outcome of GOSE at 6 months between two treatment arms. Interim analyses will be performed after 31, 60, 120, 180, 240, and 300 patients randomized. The 0.02 significance level has been calibrated to adjust for the multiple interim analyses and maintain an overall study type I error rate below 0.025. At each interim analysis, we will evaluate the predictive probability of statistical significance with the current sample size and with the maximum sample size. If the predictive probability of statistical significance with the current sample size is sufficiently high, then enrollment will stop and follow up will continue for 6 months. If the predictive probability of statistical significance with 350 patients is sufficiently low, then the study will stop for futility. Otherwise, enrollment will continue to the next analysis.

# 9.4 Data Monitoring

A Data and Safety Monitoring Board (DSMB) will be established. The DSMB will include a biostatistician with expertise in research design and an expert in management of brain injured patients. Site PIs will monitor safety of each enrolled subject. In addition, safety analysis will be ongoing with interim monitoring for safety and study performance for every 20 patients or at least annually following the randomization of the first subject. Interim analysis for consideration of discontinuing the study for futility or discontinuing enrollment for predicted success will be performed after 31, 60, 120, 180, 240, and 300 patients have been randomized. Enrollment will be ongoing during this assessment.

Authorized representatives of the US Army Medical Research and Materiel Command (USAMRMC), who is one of the funding agency for this study, may review or obtain identifiable information (including the case ID number) related to participation in this research study for the purpose of monitoring the accuracy and completeness of the research data, for performing required scientific analyses of the research data, and as part of their responsibility to protect human research volunteers.

# 9.5 Data Analyses

The primary analysis population will be an Intention-to-Treat population, all randomized subjects, followed by an As-Treated analysis for sensitivity. As described below, for the primary outcome, 4-week DRS will be used to impute missing 6-month GOSE for the interim analyses. Demographic and baseline laboratory results will be summarized using descriptive statistics, including means, standard deviations, medians, ranges, histograms and box-plots. Fisher's exact test and Wilcoxon rank sum test will be used in the data analyses of categorical and continuous variables, respectively. Adverse events will be reported by type, frequency and severity.

9.5.1 Statistical Modeling. The National Acute Brain Injury Study: Hypothermia II (NABIS:H II) shows that there was a strong correlation between 4-week Disability Rating Scale (DRS) and 6month GOSE (Table 1). In particular, there were 2 false negatives out of 45 patients (4%) and 6 false positives out of 30 patients (20%). It shows that the short-term response is a good predictor for 6-month GOSE.

Table 3 summarizes the historical data (NABIS:H II study) comparing the 4-week DRS score and 6-month outcome; 80% (24/30) of good short-term DRS had a good long-term GOSE, while 4% (2/45) poor DRS had a good GOSE:

Table 3

	6-month GOSE		
4-week DRS Score	Poor	Good	Total
Poor (19 or larger)	43 (96%)	2 (4%)	45
Good (18 or less)	6 (20%)	24 (80%)	30

The statistical model used in this study explicitly models the relationship between 4-week DRS and 6-month GOSE score. Let pDc and pDt be the probabilities of good 4-week DRS scores in the control and treatment groups. Furthermore, define

 $p_{Gc0} = Pr(GOSE good | control, DRS poor)$ 

 $p_{Gc1} = Pr(GOSE good | control, DRS good)$ 

pGt0 = Pr(GOSE good | treatment, DRS poor)

pGt1 = Pr(GOSE good | treatment, DRS good)

These probabilities define the conditional probabilities of achieving a good GOSE score given the DRS score and treatment group.

Together, pDc, pDt, pGc0, pGc1, pGt0, and pGt1 define a joint distribution over DRS and GOSE scores. The key parameter of interest is the probability of a good GOSE score within each group, which can be derived from these parameters.

We estimate these parameters in a Bayesian fashion, placing Beta(2,3) priors on pDc and pDt, Beta(1,4) priors on pGc0 and pGt0, and Beta(4,1) priors on pGc1 and pGt1. These priors reflect the historical data but are weak in that each prior has 5 observations worth of weight, meaning that accumulating data in contrast to the historical data above will result in inferences based on the current data, not the historical data. Thus this model is sufficiently flexible that it may be used when DRS is highly predictive of GOSE and also may be used if DRS is not predictive of GOSE.

The final analysis is a one-sided Fisher exact test with significance level 0.02 conducted only on the GOSE scores. Thus, the DRS values are only used in the analysis to predict GOSE scores for subjects who have a DRS score but not a GOSE score. For the final analysis, 6-month GOSE scores will be used. If the 6-month GOSE score is missing the 4-week DRS score will be used to impute the 6-month GOSE score.

At each interim analysis we compute two predictive probabilities. The first is the predictive probability of trial success if enrollment stops, the current subjects are followed to completion, and the Fisher's exact test is conducted on the final data. For this predictive probability many of the subjects will have 6-month GOSE scores reported. The uncertainty in the predictive

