#### 5. STUDY INTERVENTIONS

#### 5.1 Interventions, Administration, and Duration

This is a pragmatic study; patients will be treated with standard care as established at each enrolling center. All of the enrolling sites utilize Brain Trauma Foundation Guidelines as foundation for delivery of care(40). Intravascular cooling catheters may be placed in the emergency room, the operating room or neurotrauma intensive care unit (NTICU). Patients randomized to hypothermia will be rapidly cooled to 35°C before opening the dura and then maintained at 33°C±0.5°C for a minimum of 48 hours and a maximum of 5 days. After evacuation of SDH all patients will be cared for in the ICU by teams experienced in hypothermia and the management of TBI.

Intravascular cooling will be provided by CoolGard 3000 or Thermogard XP which use an intravenous central catheter circulating cooled saline in a closed loop system. These devices

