Following placement of the electrode, the lead will be externalized through the dura and craniotomy. If the bone flap is replaced, the lead will be exteriorized through a burr hole to facilitate subsequent removal. Furthermore, the lead wire will be exteriorized in a straight line with the electrode strip, also to facilitate removal. Finally, the lead is tunneled under the scalp and out through a stab wound distant from the craniotomy incision line in order to reduce the risk of infection. When ECoG recordings are complete, the strip is removed by gently pulling it through the stab wound followed by watertight closure of the skin incision.

The technique of ECoG strip placement is a standard surgical procedure in epilepsy neurosurgery, and has been used as described to monitor surgical patients with severe stroke or traumatic brain injury at more than a dozen neurosurgical centers.(41-45)

Upon admission to the neuro-intensive care unit (NICU), following surgery, the leads from the ECoG electrode strip will be connected to an EEG amplifier. External ground and reference electrodes will be placed and continuous ECoG recordings will then commence. The reference electrode is a platinum needle placed under the scalp.

Continuous ECoG monitoring will be performed for at least the same duration as ICP monitoring. In patients randomized to hypothermia, this is until at least 24 hours after re- warming is complete. In normothermia patients, patients will be monitored a minimum of 96 hours, and longer if continued ICP monitoring is clinically indicated. When monitoring is complete, the electrode strip will be removed at the bedside under sterile conditions, as is performed for standard-of-care intracranial devices.

Blood samples for biomarker analysis will be taken at 3 time points (T1, within 6 hrs and as close to time of injury as possible (pre-hypothermia for the treatment arm); T2, post-surgical evacuation of hematoma (7-48 hrs); T3, 5-14 days post-injury or DC whichever comes first. If the patient has a ventricular drain in place, CSF samples will also be collected.

As part of standard care all patients are expected to have an intracranial pressure monitor (either extraventricular drain or intraparenchymal monitor).

**5.3.2 Prohibited Interventions.** Please see re-warming protocol regarding fluids and electrolytes.

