The operating characteristics of this design (type I error, power, and expected sample size) were computed by simulation in a variety of possible scenarios. These scenarios were constructed by crossing four possible treatment effects with two possible relationships between 4-week DRS and 6-month GOSE scores (predictive and nonpredictive). Table 5 shows the values of the parameters for each of the simulated scenarios. In all scenarios the probability 6- month GOSE is good in the control arm is 0.347. In the *null* scenarios, scenarios where there is no difference between the scores, the probability 6-month GOSE is good in the treatment arm is also 0.347 (no treatment effect). We also consider low scenarios where the probability 6-month GOSE is good in the treatment arm is 0.498, medium scenarios where the probability 6-month GOSE is good in the treatment arm is 0.536, and alternative scenarios where the probability 6- month GOSE is good in the treatment arm is 0.604. The trial is powered for values closer to the 0.604 6-month scenario.

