#### 11.4 Risk Analysis

Biocompatibility, bench, animal, other clinical studies (IDE 990263) and long-term use in humans have all shown that the ZOLL IVTM System appears to be safe for use. The system is made of materials that are commonly used in other medical devices with comparable applications and all materials have been tested in accordance with ISO 10993-1. All components of the ZOLL IVTM Catheters and ZOLL Thermogard XP System, and accessories have been cleared for commercial use by the FDA under 510(k) (K101987 and K072234).

Increased Risks and Benefits to Study Participants Elevated ICP secondary to TBI which is associated with increased morbidity and mortality is responsive to hypothermia. Increasingly, therapeutic hypothermia is used to treat refractory intracranial hypertension in TBI. Additionally, experimental evidence suggests induced hypothermia of 32-35°C early post injury may be neuroprotective. It is this early neuroprotective effect of hypothermia that is therapeutic aim of this study. TBI resulting in SDH occurs in over 40,000 Americans annually with up to 70% of these injuries resulting in death or severe disability(27). Risks associated with hypothermia may include shivering, hypovolemia, electrolyte disorders, hyperglycemia, pneumonia, and some risk of catheter-related thrombosis or possible catheter-related infection with intravascular cooling devices. Risks are minimized by reaching the goal temperature as quickly as possible, rewarming slowly and removing the intravascular catheter within 5 days of placement (33). Risk is relative in an entity with high mortality, and may be considered relative to a procedure that may increase the chances of good neurological outcome. The risk of ECoG brain activity monitoring includes the risk of infection or bleeding in approximately 1-5%, but no such complications have been observed previously in similar patients who have undergone this procedure. The electrode strip will be removed at the bedside by the neurosurgeon. There is approximately a 1-2% risk for difficulty in removing the strip.(43)

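### The only sensitivity analysis of the primary outcome is an undefined As-Treated comparison, which can show a spurious effect in either direction if switching follows prognosis

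*Combined protocol and SAP*

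**What the plan says.** Section 9.5 sets the populations: "The primary analysis population will be an Intention-to-Treat population, all randomized subjects, followed by an As-Treated analysis for sensitivity". The study schematic repeats both. Neither place gives a temperature, timing or duration that makes a patient *treated*, and no adjustment is planned. The primary test is stated separately: "The final analysis is a one-sided Fisher exact test with significance level 0.02 conducted only on the GOSE scores".

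On leaving the assigned treatment:

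- **Hypothermia arm.** Section 8: "Subjects may be discontinued from hypothermia at any time for patient safety per the decision of the site PI". Under section 6.3.1, refusal of permission to continue also leads to rewarming. Section 6.2.3 keeps patients who stop in follow-up.
- **Control arm.** The synopsis and section 3 set 37°C ±0.5°C, and section 5.3.1 lists normothermia at 37°C among the required interventions. Background care is local. Section 5.1: "This is a pragmatic study; patients will be treated with standard care as established at each enrolling center". Section 11.4 remarks: "Increasingly, therapeutic hypothermia is used to treat refractory intracranial hypertension in TBI". The whole entry under prohibited interventions (5.3.2) is "Please see re-warming protocol regarding fluids and electrolytes". No section says what happens to a control whose ICP is refractory.

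On adherence, section 5.4 analyses time to goal, duration of cooling and temperature range by group. Section 6.3.5 has every change to hypothermia or normothermia recorded with its reason, and 6.3.9 monitors temperature against assignment.

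**The concern.** An As-Treated analysis compares patients by what they received. If the reason for switching is linked to outcome, the groups differ in prognosis and the comparison is no longer randomised. Both routes here could have that link. Stopping hypothermia for safety would tend to remove unstable patients from the hypothermia group. Cooling a control for refractory ICP would add a poor-prognosis patient to it. The first makes hypothermia look better than it is; the second makes it look worse.

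The missing definition adds to this. A patient cooled to 35°C and then stopped is treated under a rule based on reaching 35°C, but not under one requiring 48 hours. A control cooled on day 3 could be placed in either group. As written, the choice could be made after the data are seen.

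At stake is the reading of the primary result. If switching dilutes the ITT difference, readers will turn to the sensitivity analysis, and it could contradict a sound ITT result or lend it false support.

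**Working it through.** **Inputs from the documents.** Section 9.5.2: "In all scenarios the probability 6- month GOSE is good in the control arm is 0.347", and "alternative scenarios where the probability 6- month GOSE is good in the treatment arm is 0.604". The test is one-sided Fisher at 0.02, allocation is 1:1, and N is 120 intended and 350 at most (9.3).

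**Assumptions, because the documents give no figures.** The share of one arm that switches is f. The proportion of those movers with a good outcome is g. As-Treated is taken to use the same test as the primary analysis.

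**Step 1: reproduce the plan's figures.**

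- Table 5 control rate: 0.40 × 0.800 + 0.60 × 0.045 = 0.347. Alternative: 0.74 × 0.800 + 0.26 × 0.045 = 0.604.
- Simulating the adaptive design at an assumed 2 patients per month gives power of 0.945 and 0.926 in the predictive and non-predictive alternative scenarios. Table 6 states 0.942 and 0.917. At 8 per month the second falls to 0.854, so the match depends on accrual. The plan's power figures are not in dispute here.

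**Step 2: As-Treated difference with no treatment effect.** Let p = 0.347 in both arms and let a share f of one arm move.

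- Patients left in the source group: (p − fg)/(1 − f)
- Receiving group: (p + fg)/(1 + f)

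For f = 0.10, g = 0.10: (0.347 − 0.010)/0.90 = 0.374 and (0.347 + 0.010)/1.10 = 0.325, a gap of 5.0 points.

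| Movers' good-outcome rate g | f = 10% | f = 15% | f = 20% |
|---|---|---|---|
| 0.10 | 5.0 | 7.6 | 10.3 |
| 0.20 | 3.0 | 4.5 | 6.1 |
| 0.347 (average prognosis) | 0 | 0 | 0 |

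The gap favours hypothermia when hypothermia patients move out, and is against it when controls move in. With f = 5% and g = 0.10 it is 2.5 points. If both arms switch at the same f with the same g, each regrouped rate is (p − fg + fg)/(1 − f + f) = p, so the gap is 0.

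**Step 3: how often As-Treated would reach one-sided 0.02 with no effect (simulation, g = 0.10).**

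| Crossover | N = 120 | N = 350 |
|---|---|---|
| None | about 0.013 | about 0.015 |
| 10% of hypothermia arm moves: false benefit | 0.048 | 0.113 |
| 20% of hypothermia arm moves: false benefit | 0.137 | 0.424 |
| 10% of controls move: false harm | 0.046 | 0.115 |
| 20% of controls move: false harm | 0.138 | 0.416 |

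With g = 0.20 and 20% moving, the rate at N = 120 is about 0.06 in either direction. ITT stayed at 0.012–0.015 at N = 120 under every pattern tried.

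**Step 4: what switching does to ITT.** Suppose movers take the other arm's rate in the non-predictive alternative scenario, at 2 patients per month. Adaptive power is then 0.924 with no switching, 0.870 with 5% in each arm, 0.814 with 10% and 0.593 with 20%. ITT loses power but keeps its error rate.

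**Step 5: why the definition of receipt matters for the replacement.** A complier-average effect is the ITT difference divided by the between-arm difference in receipt. Take a 15-point ITT difference (the size in section 1.1), all hypothermia patients cooled early, and 20% of controls cooled late. If any cooling counts as receipt, the estimate is 15/(1 − 0.20) = 18.75 points. If only early induction counts, it is 15/(1 − 0) = 15 points.

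**The case against.** A reader might infer that nothing stops controls being cooled. The documents do not support that: normothermia within 0.5°C of 37°C is required, and the control catheter is there to maintain it. The remark in 11.4 describes TBI practice in general, not these sites' controls. What stands is narrower: no section covers a control with refractory ICP, and local standard care may pull against the target.

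A reader might also infer that As-Treated is the only check on crossover. It is not. Sections 5.4, 6.3.5 and 6.3.9 provide adherence analysis and records, and 10.3 has protocol deviations reviewed monthly. None of these is linked to the Glasgow Outcome Scale-Extended (GOSE), so As-Treated remains the only outcome analysis that bears on switching.

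The size is open to challenge. The documents give no crossover rate and no prognosis for movers, the two routes can cancel, and the design is powered for 25.7 points (0.604 − 0.347), not 15. All of that is fair, and it is why the figures are an illustration. But nothing in the plan ensures balance, and a reader of the results could not tell whether it had occurred.

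Finally, a complier-average effect tests the same null as ITT, so it adds no protection against a false positive that ITT lacks. That is true. Its use is to estimate the effect of receiving the intervention without giving up randomisation, which As-Treated cannot do.

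**Conclusion.** The point holds for the sensitivity analysis only. It would be tempting to conclude that the trial's primary result is at risk of a false effect. It is not: the primary population is all randomised subjects, those who stop are followed, and no success criterion or stopping boundary uses As-Treated.

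The fault is that the one planned sensitivity analysis of the primary outcome does not define treatment received and is confounded if switching follows prognosis. With no true effect and one-way crossover of 10–20%, it would show 5.0–10.3 points if movers have 10% good outcome and 3.0–6.1 points if they have 20%. The direction is set by which arm switches more. The difference is 0 if movers have average prognosis or crossover is balanced with the same prognosis. These figures rest on assumed crossover shares and mover outcomes. The documents do not show that crossover is likely in either arm, only that both routes are left open.

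**What to change.** - **Section 9.5 and the schematic.** Label As-Treated as descriptive only. Make the adherence sensitivity analysis a complier-average causal effect: the ITT difference in good GOSE divided by the between-arm difference in the proportion who received the tested intervention, with a bootstrap interval.
- **Define receipt in advance** from recorded temperatures, to match the hypothesis and inclusion criterion 5 (4.1): core 35°C reached by deliberate cooling before the dura is opened and within 6 hours of injury. As one check, repeat with any deliberate cooling to 35°C or lower, noting that this counts late-cooled controls as recipients and so enlarges the estimate.
- **Section 5.4.** Report by arm, with time and reason: controls deliberately cooled; hypothermia patients who never reached 35°C before the dura was opened; and those who stopped before 48 hours.
- **Control target.** The sponsor should reconcile the 37°C control target with local standard care for refractory ICP. No clinical rule is proposed here.

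The cost is SAP wording and one extra calculation from data that 5.4 and 6.3.5 already call for. The primary test, sample size and trial conduct do not change. The estimate will have a wider interval than As-Treated. It also assumes that allocation affects outcome only through receipt, which later cooling in either arm or early stopping may strain; the SAP should say so.

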#### 1.2 Secondary Objectives

There are four secondary objectives of the study:

**Safety Objective:** To demonstrate the safety of intravascular cooling in the management of acute traumatic SDH.

**Exploratory Objective**: To determine the effect of hypothermia on TBI biomarkers: glial fibrillary acid protein (GFAP) and ubiquitin C-terminal hydrolase (UCH-L1).

**Mechanistic Objective:** To determine if the incidence of cortical spreading depolarization is reduced in patients undergoing therapeutic hypothermia compared to patient undergoing normothermia.

**Impact on Resource Utilization Objective**: To determine the effect of moderate hypothermia on ICU length of stay (LOS) and hospital LOS.

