As recommended by the 2007 NINDS TBI workshop, our proposed study would be the first TBI trial to use a specific pathoanatomic injury as opposed to the Glasgow Coma Scale (GCS) as the principal inclusion criterion. Additionally, it would be the first trial to study the efficacy and safety of hypothermia induction using intravascular cooling catheters. In previous trials, hypothermia was induced via surface cooling, a technique that is associated with both significant temperature variability as well as challenges for temperature control in TBI patients requiring emergent neurosurgical operations. Demonstration of safety and efficacy of hypothermia induction with intravascular cooling catheters would increase the generalizability of hypothermia as an intervention. Finally, our study could both confirm the NABIS:H I and NABIS:H II data regarding the benefit of hypothermia for TBI patients who undergo surgical evacuation of intracranial hematomas and potentially provide a mechanism to explain this phenomenon.

Significant morbidity and mortality occurs in traumatic SDH. Mortality rate estimates range from 40-70% of surgical SDH patients(27;28). SDH patients may experience elevated intracranial pressure (ICP), seizures, coagulopathy and hypotension(29-33). SDH patients enrolled in this study are expected to require mechanical ventilation and monitoring of intracranial pressure as part of their routine care(28). Risks associated with hypothermia may include shivering, hypovolemia, electrolyte disorders, hyperglycemia, pneumonia, (small risk of skin lesions if water-circulating surface cooling pads are used), and some risk of catheter-related thrombosis

or possible catheter-related infection with intravascular cooling devices. Risks are minimized by reaching the goal temperature as quickly as possible, rewarming slowly and removing the intravascular catheter within 5 days of placement(33).

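### Does the length-of-stay comparison need a rule for patients who die in hospital?

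*Combined protocol and SAP*

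**What the plan says.** Section 1.2 lists LOS as the fourth secondary objective. It is headed "Impact on Resource Utilization Objective" and reads "To determine the effect of moderate hypothermia on ICU length of stay (LOS) and hospital LOS". Section 9.2.2 repeats it as an outcome by name only: "ICU LOS, hospital LOS".

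Section 9.5 does not mention LOS. Two of its general statements would apply. The first is the choice of tests: "Fisher's exact test and Wilcoxon rank sum test will be used in the data analyses of categorical and continuous variables, respectively". The second is the population: "The primary analysis population will be an Intention-to-Treat population, all randomized subjects". The natural reading, which is an inference, is a Wilcoxon test on days in everyone randomized, deaths included.

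On mortality, section 2.2 says "Mortality rate estimates range from 40-70% of surgical SDH patients". Section 9.2.1 fixes where death sits on the outcome scales: it is a poor GOSE outcome, and for the DRS "Scores range from 0 (no disability) to 29 (profound vegetative state) and death is scored at 30". Section 7 makes death the first-named safety comparison: "Primary focus for analysis will be on 6-month mortality rate". Section 9.5.3 monitors deaths by arm.

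**The concern.** A patient who dies on day 3 has a three-day stay. In a rank test on raw days that counts as a short stay, next to a survivor who went home quickly. With mortality as high as section 2.2 cites, many stays could end this way. If hypothermia saved lives, its arm could show longer stays and the result be taken as a cost or a harm. If it caused early deaths, its arm could show shorter stays and the result be taken as a benefit.

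The plan gives death a place on GOSE and DRS but not in LOS, so the omission looks like an oversight. It also appears to leave a choice between raw days, survivors only and a death-aware score until the data are known.

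**Working it through.** The plan states no LOS figure (no effect size, spread or power), so there is nothing of its own to reproduce. The check asks how far a mortality difference alone can move the Wilcoxon comparison.

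**Inputs from the documents.** Mortality of 40-70% (section 2.2); death proportions such as 0.125 vs 0.025 and 0.10 vs 0.20 (Table 7); 60 per arm at the intended N=120. I add 30 per arm (the N=60 look) and 15 per arm (about the size of the 31-subject look).

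**Assumptions.** Log-normal stays, identical in both arms among survivors and among deaths. Survivor median 14 days (SD of log 0.5). Median time to death m = 4, 8 or 12 days (SD of log 0.7). Every death in hospital, which maximises the effect. Mortality difference 10 points. Two-sided test at 0.05.

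**Step 1.** Chance that a survivor's stay exceeds the stay of a patient who dies: w = Φ(ln(14/m) / √(0.5² + 0.7²)), where the root is 0.860.

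**Step 2.** Let θ be the chance that a random patient in the lower-mortality arm stays longer than one in the other arm. Pairs of two survivors or two deaths contribute one half each, so θ − ½ = (difference in mortality) × (w − ½). With equal mortality this is zero.

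**Step 3.** With n per arm, z = (θ − ½) × √(12n² / (2n+1)). The root is 9.33, 13.31 and 18.89 for n = 15, 30 and 60. The share of trials in which the lower-mortality arm is significantly longer is P(Z > 1.96 − z).

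| m (days) | w | θ − ½ | n=15 | n=30 | n=60 |
|---|---|---|---|---|---|
| 4 | 0.927 | 0.0427 | 5.9% | 8.2% | 12.5% |
| 8 | 0.742 | 0.0242 | 4.2% | 5.1% | 6.7% |
| 12 | 0.571 | 0.0071 | 2.9% | 3.1% | 3.4% |

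For m = 4 and n = 60: z = 0.0427 × 18.89 = 0.807, and P(Z > 1.153) = 12.5%.

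**Simulation.** With 20,000 trials per cell, over mortality pairs from 70 vs 60% down to 12.5 vs 2.5%, the shares at 15 / 30 / 60 per arm agree:

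- deaths at 4 days: 5.7-6.1% / 8.0-8.2% / 12.1-12.5%
- deaths at 8 days: 4.0-4.3% / 4.8-5.0% / 6.5-6.6%
- deaths at 12 days: 2.8-3.0% / 2.8-3.1% / 3.2-3.7%
- equal mortality: 2.2-2.7% per side

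At 50 vs 40% mortality the median stays differ by at most 1.4 days (deaths at 4 days) and by 0.2 days with deaths at 12 days. At the maximum of 175 per arm and deaths at 4 days the share is 27.5-29.0%, but Table 6 puts the chance of reaching N=350 at only 1-13%.

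**A death-aware score instead.** If death takes the worst rank, timing drops out and θ − ½ = 0.10 × ½ = 0.05, more than in any row above. Ties among deaths divide the standard error by a further factor: z is multiplied by 1/√(1 − p̄³), where p̄ is the average mortality. At 50 vs 40% and n = 60, z = 0.05 × 18.89 / √(1 − 0.45³) = 0.945 / 0.953 = 0.991, and P(Z > 0.969) = 16.6%. Simulation gives 15-17% (20% at 70 vs 60%). Free days to day 28 with death scored 0 gives 13-15% (18% at 70 vs 60%).

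**The case for a change.** The best case for a change is prespecification. Death may end a large share of stays, the protocol gives death a place on its other scales, and a few lines would remove any later choice of method. The effect can also be larger than in the table. With survivor median 20 days, log-SD 0.6 and a 15-point difference (40 vs 55%), 60 per arm, raw days are significant in the direction of fewer deaths meaning longer stays in 17-28% of simulated trials. The formula agrees at the upper end: w = Φ(ln 5 / 0.849) = 0.971, z = 0.15 × 0.471 × 18.89 = 1.33, share about 27%.

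What stands: the rule is not written down, and this is not an artefact of redaction. The direction of the shift is certain whenever mortality differs and deaths precede discharges.

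What does not stand is the step from there to a flawed analysis. The objective is resource use, and a bed occupied until death is a bed used. The plan nowhere offers LOS as a measure of patient benefit. The population statement already points to everyone randomized, so a survivors-only comparison would be a departure from the plan. A mortality difference large enough to move LOS would appear in the mortality analysis that section 7 puts first.

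**Conclusion.** No change is needed. This is missing detail that analysts would fill sensibly: bed-days in all randomized patients, by the planned Wilcoxon test, read beside mortality by arm. That answers the stated question. The possible harm is a later misreading of LOS as benefit or harm, not an error the plan commits.

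The size is modest. For a 10-point mortality difference the excess over the 2.5% chance level is 0.3 to 5.7 points at 15-30 per arm (2.8-8.2%) and 0.7 to 10 points at 60 per arm (3.2-12.5%). It vanishes with equal mortality and nearly so if deaths occur about as late as discharges. These figures rest on assumed stay and time-to-death distributions, because the documents give none; larger differences or longer survivor stays raise them.

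The only new method on offer, a death-aware composite, is a trade-off on which statisticians differ. It responds to mortality more than raw days do and largely duplicates a comparison already planned, so it would not give a cleaner answer about resource use. The primary GOSE test, the sample size and the stopping rules do not depend on this point.
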